1.0 SYNOPSIS

Title:	AMPLATZER™ Cardiac Plug Observational Post-Approval Study
Acronym:	ACP PAS China
Purpose:	To observe the safety and effectiveness of the AMPLATZER™ Cardiac Plug (ACP) device in Chinese population indicated for use of AMPLATZER™ Cardiac Plug after its market approval by China FDA (CFDA).
Objectives:	
Primary Objectives
 
(1) To evaluate short term (0 - 7 days post-procedure) safety of AMPLATZER™ Cardiac Plug implantation in Chinese population(2) To evaluate long term safety of AMPLATZER™ Cardiac Plug implantation in Chinese population through 2 years(3) To evaluate effectiveness of AMPLATZER™ Cardiac Plug implantation in Chinese population through 2 years 
Additional Objectives
 
(1) To evaluate the occurrence of ischemic stroke or systemic embolism through 5 years in Chinese population implanted with AMPLATZER™ Cardiac Plug(2) To evaluate long term safety of AMPLATZER™ Cardiac Plug implantation in Chinese population through 5 years(3) To evaluate immediate successful implantation rate of the AMPLATZER™ Cardiac Plug in the left atrial appendage (LAA) during the procedure
Endpoints:	
Primary Endpoints
 
1. Short Term Safety Major adverse events within 7 days after the procedure: short term occurrence of death, stroke (ischemic or haemorrhagic), systemic embolism, or procedure or device-related complications requiring major cardiovascular or endovascular intervention.2. Long Term Safety The 2-year occurrence of device embolization, device erosion, clinically significant device interference with surrounding structure, device thrombus, device fracture, device infection (endocarditis / pericarditis), device perforation, device laceration, or device allergy.3. Effectiveness The 2-year rate of the composite of ischemic stroke or systemic embolism 
Descriptive Endpoints
 
1. Rate of ischemic stroke or systemic embolism through 5 years post-implant2. Occurrence of composite of damage to blood vessel or organ or damage to adjacent organs at implant, device dislodgement, device

Clinical Investigational Plan

	
fracture, device erosion, or pericardial tamponade through 5 years post-procedure
 
3. Device success rate - defined as device deployed and implanted in correct position4. Rate of closure of the left atrial appendage - defined as residual jet around the device of $\leq 5\text{mm}$, based on the 45-day TEE
	
This is a prospective, multi-centre, single arm, post approval, observational study. The clinical study will be conducted at up to 35 sites in China. Approximately 343 subjects will be enrolled in this study.
 
(1) Patients who are eligible for an ACP based on the approved indications can be enrolled in this study.(2) Each patient will be followed up for 5 years.(3) Baseline, procedure, and pre-discharge evaluations will be required.(4) Hospital visit will be required at 45 days, 6 months, 12 months and 24 months.(5) The 36-, 48- and 60-month follow up visits will be conducted by telephone contact with proper record. 
The total study duration is expected to be approximately 7 years; this observational study will begin enrolment in Q4 of 2016.
 
Per CFDA requirement, an annual report of ADE and SADE observed in this study will be submitted to CFDA.

Design:	
Testing required:
 
▪ Baseline evaluation: Informed consent, cardiovascular and medical history, physical examination, 12-lead electrocardiogram (ECG), CHA2DS2-VASc score and individual components of the score, HAS-BLED score, Neuroimaging (brain MRI or CT scan), modified Rankin Scale and medication assessment▪ Procedure: Transesophageal echocardiogram (TEE), Angiogram, medication and adverse event (AE) assessment▪ Post procedure/Pre-Discharge: Transthoracic echocardiogram (TTE), medication assessment, AE assessment▪ 45day (+45 days): TEE, medication assessment, AE assessment▪ 6M (+/- 3 weeks): Medication and AE assessment▪ 12M and 24M (+/- 6 weeks): Medication and AE assessment▪ 36M, 48M and 60M(+/- 6 weeks): Phone contact follow-up for medication and AE assessment▪ Interim/unscheduled visits: Per subject or physician discretion 
Suspected Stroke / TIA Evaluation:

Clinical Investigational Plan

	
▪ All subjects suspected of a stroke should be seen by a stroke neurologist for evaluation and appropriate neurological testing (i.e. magnetic resonance imaging (MRI), computed tomography (CT))▪ In the event of a confirmed stroke or TIA, the modified Rankin Scale assessment should be performed 90 days after the event and a TEE should be conducted to verify the presence of device-related thrombus within 14 days from the date the site becomes aware of the event
Justification for study design	
A single-arm observational study is appropriate to observe the safety and effectiveness of the ACP device in the post-market setting in China. The study includes a short-term safety endpoint, a long-term safety endpoint, and a long-term effectiveness endpoint.
 
The safety and effectiveness endpoints in this study are consistent with those reported for other studies or publications on left atrial appendage occlusion.
 
The short-term safety endpoint was chosen to reflect serious procedure-related complications during the implant procedure for the ACP device, resulting in either surgical or endovascular intervention. This endpoint appropriately captures important procedural complications and adequately characterizes the short-term safety profile of the procedure and the device.
 
The long-term safety endpoint is set at 24 months to capture long-term complications associated with the ACP device. This safety endpoint is based on the recently released Eurointervention consensus document³⁴ on definitions, endpoints and data collection requirements for left atrial appendage occlusion clinical studies
 
Finally, the effectiveness endpoint appropriately reflects the occurrence of types of events (ischemic stroke or systemic embolism) that the device is intended to prevent. This endpoint is consistent with other studies and publications on left atrial appendage occlusion.
 
The performance goals for this study have been established primarily based on publications on the ACP device. [REDACTED] [REDACTED] [REDACTED]
 
Additional descriptive endpoints have been specified to characterize the mechanism of action of the device (i.e., device closure) and the long-term effects of device implant through 5 years.

Devices used:	The AMPLATZER™ Cardiac Plug is a transcatheter, self-expanding device intended for use in preventing thrombus embolization from the left atrial appendage. The device is constructed from a nitinol mesh and consists of a lobe and a disc connected by a central waist. The device is [REDACTED] [REDACTED]

Clinical Investigational Plan

	
designed to facilitate occlusion. The lobe has stabilizing wires to improve device placement and retention. The device has threaded screw attachments at each end for connection to the delivery and loading cables. The device has radiopaque markers at each end and at the stabilizing wires.
 
Device Sizes: 16, 18, 20, 22, 24, 26, 28, and 30 mm (lobe diameter)
 
Delivery System: AMPLATZER TorqVue® 45° x 45° (sheath sizes 9, 10, or 13 Fr)

Study Population	Patients who have non-valvular atrial fibrillation (NVAF) and are contraindicated to long-term oral anticoagulant; or patients who experience stroke or relevant event despite taking warfarin.
Inclusion/Exclusion Criteria	
Inclusion Criteria
 
• Patient who meets the current indications and per physician discretion for ACP implant• Patient who is ≥ 18 years of age at the time of enrolment.• Patient who is able to provide written Informed Consent prior to any study related procedures. 
Exclusion Criteria
 
• Patient who is unable to comply with the follow-up schedule• Patient with the presence of intracardiac thrombus• Patient with active endocarditis or other infections producing bacteraemia• Patient who has low risk of stroke (CHA2DS2-VASC score is 0 or 1) or low risk of bleeding (HAS-BLED score<3)• Patient where placement of the device would interfere with any intracardiac or intravascular structures• Patient who is under medical conditions not appropriate to participate in the study in the opinion of the investigator• Subject with LAA anatomy that does not accommodate a device per the sizing guidelines• Patient who has a life expectancy of less than 2 years due to any condition• Patient who are currently participating in a clinical investigation that includes an active treatment arm.

Clinical Investigational Plan

Clinical Investigational Plan

[REDACTED] The performance goal, PG_i , is set at 10%, [REDACTED]

[REDACTED] 308 subjects are required to be enrolled in the study.

Primary Effectiveness Endpoint:

The following hypotheses will be tested:

$$H_0: p_e \geq PG_e$$

$$H_1: p_e < PG_e$$

where p_e is the event rate at 24 months. [REDACTED]

[REDACTED] The performance goal, PG_e is set at 9%, [REDACTED]

[REDACTED] 343 subjects are required to be enrolled in the study.

[REDACTED]

Abbott

Study Document No: SJM-CIP-10153 Ver. D

Study Name: AMPLATZER™ Cardiac Plug
Observational Post-approval Study

Clinical Investigational Plan

For more information, contact the Office of the Vice President for Research and the Office of the Vice President for Student Affairs.

1000

1000

—
—

111

10

—
—

11. **What is the primary purpose of the *Journal of Clinical Endocrinology and Metabolism*?**

Clinical Investigational Plan

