7.3 SCHEDULED FOLLOW-UPS

Scheduled office visits occur at 45 days (+45 days), 6M (+/- 3 weeks) 12M (+/- 6 weeks) and 24 M (+/- 6 weeks) post procedure;

Phone contact follow up visits occur at, 36M (+/- 6 weeks), 48M (+/- 6 weeks) and 60 M (+/- 6 weeks) post procedures.

Refer to Table 2 for required follow-up testing and assessments.

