7.7 CRITERIA AND PROCEDURES FOR SUBJECT WITHDRAWAL OR DISCONTINUATION

Subjects must be informed about their right to withdraw from the study at any time and for any reason without sanction, penalty or loss of benefits to which the subject is otherwise entitled and withdrawal from the study will not jeopardize their future medical care or relationship with the investigator. Subjects will be asked to specify the reason for the termination, but have the right not to answer.

The investigator may decide to withdraw a subject from the study at any time with reasonable rationale. The subject's future care will not be influenced by a decision, voluntary or otherwise, to withdraw from the study. All reasonable efforts should be made to retain the subject in the clinical study until completion of the study.

Reasons for subject's withdrawal include, but are not limited to:

- Subject refuses to continue participating in the study
- Withdraw subjects who have an unsuccessful implant 7 days after the date of the attempted procedure.
- Subject is deceased (cause must be documented)
- Subject's non-compliance
- Subject is 'lost to follow up': Subject does not adhere to the scheduled follow up visits but has not explicitly requested to be withdrawn from the clinical study. (This does not apply to missed visits).

Site personnel should at all times make all reasonable efforts to locate and communicate with the subject in order to achieve subject compliance to the scheduled follow up visits:

1. A subject will be considered 'Lost to Follow Up' after a minimum of 2 phone calls of a physician or delegate at the investigational site to the subject or contact. These 2 phone calls need to be documented in the subject's study charts and/or medical record.
2. If these attempts are unsuccessful, a letter should be sent to the subject's last known address or general practitioner (GP) and a copy of this letter should be maintained in the subject's study charts and/or medical record.

Note: If a subject misses one or more of the scheduled follow up visits (inclusive of the assigned visit windows), this will be considered as a missed visit. The subject may therefore still return for subsequent visits and will not be excluded from the study.

If a subject withdraws from the clinical study, the site will record the subject's reasons for withdrawal, on a Withdrawal CRF.

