13.1.2 Primary safety endpoint (Long-Term)

The long-term safety endpoint is the 2-year occurrence of device embolization, device erosion, clinically significant device interference with surrounding structure, device thrombus, device fracture, device infection (endocarditis / pericarditis), device perforation, device laceration, or device allergy.

[REDACTED]

[REDACTED]

Clinical Investigational Plan

Hypothesis:

$$H_0: p_l \geq PG_l$$

$$H_1: p_l < PG_l$$

where p_l is the long-term safety endpoint event rate. It is assumed that the long-term safety endpoint event rate is 5%. [REDACTED]

[REDACTED]

[REDACTED]

[REDACTED] An event rate of 5% is assumed for the long-term safety endpoint for the ACP device [REDACTED]

[REDACTED] The performance goal, PG_l , is set at 10% [REDACTED]

[REDACTED]

[REDACTED]

[REDACTED]

Analysis Methods:

Kaplan-Meier survival analysis will be used to estimate the event rate of at 24 months (731 days post implant). [REDACTED]

[REDACTED]

Sample Size Determination:

The sample size is estimated assuming an event rate of 5%. A sample size of 231 subjects followed through 24 months will provide 80% power at the 2.5% significance level. Assuming an attrition rate of 25% through 24 months, 308 subjects are required to be enrolled in the study.

Analysis Population:

Enrolled subjects will be included in this analysis.

13.1.3 Primary effectiveness endpoint:

The primary effectiveness endpoint is the composite endpoint of ischemic stroke or systemic embolism at 2 years.

Hypothesis:

$$H_0: p_e \geq PG_e$$

$$H_1: p_e < PG_e$$

where p_e is the event rate at 24 months. [REDACTED]

[REDACTED]

[REDACTED]

[REDACTED] The performance goal, PG_e is set at 9%, [REDACTED]

[REDACTED]

[REDACTED]

Analysis Methods:

[REDACTED]

Clinical Investigational Plan

Kaplan-Meier survival analysis will be used to estimate the event rate of at 24 months (731 days post implant). XXXXXXXXXX

Sample Size Determination:

A sample size of 257 subjects followed through 24 months will provide 80% power at the 2.5% significance level assuming a 24-month event rate of 4.5%. Assuming an attrition rate of 25% through 24 months, 343 subjects are required to be enrolled in the study.

Analysis Population:

Enrolled subjects who receive an implant of the ACP device will be included in the analysis.

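### The 6-, 12- and 24-month visits collect only what is later collected by telephone, but they require attendance with no remote fallback, leaving an avoidable ascertainment gap in the window of both 2-year primary endpoints

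*Combined protocol and SAP*

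**What the plan says.** **Mode of visit.** The synopsis (Design) says "Hospital visit will be required at 45 days, 6 months, 12 months and 24 months". Section 7.3 agrees: "Scheduled office visits occur at 45 days (+45 days), 6M (+/- 3 weeks"), followed by 12 and 24 months, all as office visits. Telephone contact is reserved for later years: "36M, 48M and 60M(+/- 6 weeks): Phone contact follow-up for medication and AE assessment".

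**Content of visit.** The synopsis lists "6M (+/- 3 weeks): Medication and AE assessment" and "12M and 24M (+/- 6 weeks): Medication and AE assessment". Table 2 marks the same two rows, and no others, at 6, 12 and 24 months and at 36, 48 and 60 months. Table 3 assigns the same two forms, Follow Up and Medication, to all of these visits. The 45-day visit is different, because it includes a transesophageal echocardiogram.

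**Non-attendance.** Section 7.7 says "If a subject misses one or more of the scheduled follow up visits (inclusive of the assigned visit windows), this will be considered" a missed visit. It adds that the subject may come back for later visits and stays in the study. The same section lists "Subject's non-compliance" among the reasons for withdrawal and does not define it. Section 8.2 gives failure to attend as an example of a deviation beyond the investigator's control, which must still be reported on a form.

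**Analysis.** Sections 13.1.2 and 13.1.3 estimate both 2-year primary endpoints by Kaplan-Meier at 731 days. The effectiveness goal is 9%, with an assumed rate of 4.5%, 80% power and a 2.5% significance level, and 257 subjects followed. Section 13.1.3 then states: "Assuming an attrition rate of 25% through 24 months, 343 subjects are required to be enrolled in the study". Section 13.4 requires all three primary endpoints to be met.

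**The concern.** The plan accepts telephone ascertainment for the descriptive 5-year endpoints but offers no such fallback in the first two years, when follow-up bears on the success decision. Nothing listed at 6, 12 or 24 months needs the subject to be physically present.

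Inability to travel is unlikely to be unrelated to outcome in this population, since disability after a stroke is one obvious cause. Kaplan-Meier estimation relies on censoring that carries no information about the event. If a subject stops attending because of an event treated elsewhere, and the site never hears of it, the event is not counted and the estimated rate is too low. With one arm and a fixed performance goal there is no comparator in which the same loss could offset this, so under-ascertainment pushes only towards success.

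**Working it through.** **1. Visit content and mode side by side** (synopsis, 7.3, Tables 2 and 3)

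| Visit | Assessments | Forms | Mode |
|---|---|---|---|
| 6, 12, 24 months | Antithrombotic medication, AEs | Follow Up, Medication | Attendance required |
| 36, 48, 60 months | Antithrombotic medication, AEs | Follow Up, Medication | Telephone |

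The content is identical and the mode differs. No readable passage allows a telephone, home or proxy contact to count as a 6-, 12- or 24-month visit.

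**2. What follows for a subject who cannot travel**
- Certain: a missed visit (7.7) and a reported deviation (8.2).
- Possible: withdrawal for non-compliance. The loss-to-follow-up bullet in 7.7 expressly sets missed visits aside; the non-compliance bullet does not.
- Not implied: automatic exclusion, because the note in 7.7 keeps the subject in the study.

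**3. The plan's own figure**

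Inputs from 13.1.3: goal 9%, assumed rate 4.5%, 2.5% level (taken as one-sided), 80% power, 25% attrition. Method: an exact binomial test, used to approximate the planned Kaplan-Meier test.
- Pass limit: the largest c with P(X ≤ c | 257, 0.09) ≤ 0.025. This is c = 14, with P = 0.0241.
- Power: P(X ≤ 14 | 257, 0.045) = 0.815. The first sample size to reach 80% is 257.
- Enrolment: 257 / (1 − 0.25) = 342.7, so 343. This allows for 343 − 257 = 86 subjects lost.

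The stated 257 and 343 both reproduce, and no sample-size correction is needed.

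**4. Illustration of unseen events**

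Suppose the true 2-year rate is 9%, exactly at the goal, and a fraction f of events is never known to the site. The chance of passing is then P(X ≤ 14 | 257, 0.09 × (1 − f)).

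| f (assumed) | Observed rate | Chance of passing |
|---|---|---|
| 0 | 9.00% | 2.4% |
| 2% | 8.82% | 3.0% |
| 5% | 8.55% | 4.1% |
| 10% | 8.10% | 6.9% |

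No value of f comes from the documents. The calculation is also stylised: 257 is the number followed through 24 months, whereas unseen events would arise mainly among subjects who stopped attending. It shows direction and sensitivity and does not estimate the bias.

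**The case against.** The strongest reply is that event capture does not depend on attendance, and most of that reply stands.

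- **Continuous reporting.** Section 9.2 collects AEs throughout the study and requires serious events to be reported within 3 working days of awareness. A disabling ischemic stroke is itself the effectiveness event. Once the site knows of it, later attendance does not matter for that endpoint. A reader might infer that such strokes are lost because the subject cannot travel; the documents do not support that.
- **Tracing.** Section 7.7 requires at least two documented calls to the subject or a contact before loss to follow-up is declared, and a letter to the last address or the general practitioner if they fail. Calls of this kind would often reveal a stroke. A subject who misses month 24 but stays in the study is also telephoned at 36 months.
- **Withdrawal.** A reader might infer that non-attendance leads to withdrawal, or that 7.7 contradicts itself. Neither is established. Non-compliance is undefined, the note keeps subjects with missed visits in the study, and sites must make reasonable efforts to retain them. This is an ambiguity that a site could read the wrong way.
- **Design choice.** In-person follow-up during the primary window is defensible. Patients unable to comply with the schedule are excluded at entry (5.5.2), although that cannot prevent later disability.
- **Unreadable text.** Text after the Kaplan-Meier sentences in 13.1.2 and 13.1.3 is redacted, as are 13.3 in part and some appendices, and Figure 2 is not shown. The censoring rule cannot be read, and the absence of a remote option is judged on the readable text.

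What survives is narrower. The tracing calls serve to restore attendance and to define loss to follow-up. Nothing says that a call which reaches the subject or family completes the AE and medication assessment for that visit.

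**Conclusion.** The point holds as an inexpensive improvement. Three visits in the primary-endpoint window require attendance for assessments that the plan itself collects by telephone later. A subject who cannot attend is therefore left with a missed visit and a deviation where a usable assessment could have been obtained. The residual risk is confined to events the site never learns of and to censoring that may be related to outcome. Both would favour success against the fixed goals.

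The size cannot be estimated from the documents. The illustrative rise from 2.4% to 3.0%, 4.1% or 6.9% rests on assumed unseen fractions of 2%, 5% and 10%, a true rate exactly at the 9% goal, and a binomial stand-in for the Kaplan-Meier test. A reader might go further and infer a large inflation of false success, or attribute the planned 25% attrition to the attendance rule. The documents give no basis for either: no unseen fraction is stated, and the attrition is not broken down by cause. Section 7.7 also counts deaths and unsuccessful implants as withdrawals.

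**What to change.** In the synopsis, section 7.3 and Table 2, keep hospital attendance as the default at 6, 12 and 24 months and add a fallback along these lines: *Where the subject cannot attend, the medication and AE assessment is done within the visit window by telephone with the subject or, if the subject cannot respond, with a family member or treating physician, and is recorded as a completed remote visit.*

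In section 7.7, state that missed visits alone do not count as non-compliance for the purpose of withdrawal, in line with the note already there.

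The cost is protocol wording. Sites run the same telephone assessment from 36 months, with the same two forms, and already make tracing calls. Endpoints, sample size and treatment are unchanged. The downside is that a telephone assessment is less complete than a hospital visit, but here it replaces a missing assessment. Recording the mode of contact would let the report show how many assessments were remote.

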2.0 INTRODUCTION

This document is a clinical investigational plan for St. Jude Medical's AMPLATZER™ Cardiac Plug (ACP) device post-approval observational study in the Chinese population. China FDA (CFDA) approved the ACP device in Sep 2015 and required a post-approval study of the ACP device to observe the safety and effectiveness of the ACP device in Chinese population indicated for use of ACP device after its market approval. The sponsor of this study is St. Jude Medical Coordination Center BVBA.

